8.2. Reporting Period

For SAEs, the active reporting period to Pfizer or its designated representative begins from the time that the subject provides informed consent, which is obtained prior to the subject's participation in the study, ie, prior to undergoing any study-related procedure and/or receiving investigational product, through and including 28 calendar days after the last administration of the investigational product. SAEs occurring to a subject after the active reporting period has ended should be reported to the sponsor if the investigator becomes aware of them; at a minimum, all SAEs that the investigator believes have at least a reasonable possibility of being related to investigational product are to be reported to the sponsor.

- AEs (serious and non-serious) should be recorded on the CRF from the time the subject has taken at least 1 dose of investigational product through the subject's last visit.

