8.2.4. Safety Analyses

The primary analysis is the analysis of safety.

That is, all safety data will be summarized descriptively by initial treatment group and combined Tofacitinib group of A3921139 in the safety analysis set. The adverse event data will be summarized for entire treatment duration.

A listing of subjects with dose reduction due to PE risk factors will be provided.

Incidence Rates (IR) of Adverse Events of Special Interest will be provided. Confidence intervals (95%) will be computed using exact Poisson method.

In general, IR will be calculated only for discrete (0/1) endpoints determined by adverse event data for events of special interest only. The numerator will be the number of unique subjects with a treatment emergent event as defined above during the interval from the first dose in Study A3921139 to last dose of tofacitinib + 28 days at risk period. The denominator of the incidence rate is person time accruing from the subject's first dose of tofacitinib in Study A3921139 to last dose of tofacitinib + 28 days, or to the date of the first event, whichever occurs earlier. For a subject who died, the time will be the minimum of (the date of the last dose + 28 days, or death date).

However, for mortality, malignancies (excluding NMSC and NMSC) and MACE related endpoints, all events regardless of their onset within 28 days or beyond after the last dose of tofacitinib will be included.

The concept of 28 days is applied to subjects without events that discontinued or completed the study. For ongoing subjects, 28 days will not be added to the exposure.

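### Incidence rates for death, malignancy and MACE count events at any time after the last dose, but the person-time stops at last dose + 28 days

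*SAP*

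**What the plan says.** SAP 8.2.4 makes safety the primary analysis and plans incidence rates with exact Poisson 95% limits for adverse events of special interest. The rules are:

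- **Numerator, general:** "the number of unique subjects with a treatment emergent event", within the period from first dose to last dose + 28 days.
- **Denominator:** person-time from "first dose of tofacitinib in Study A3921139 to last dose of tofacitinib + 28 days", or to the first event if that comes earlier.
- **Deaths:** for a subject who died, "the time will be the minimum of (the date of the last dose + 28 days, or death date").
- **Exception:** for mortality, "malignancies (excluding NMSC and NMSC) and MACE related endpoints", the SAP states that "all events regardless of their onset within 28 days or beyond after the last dose of tofacitinib will be included".
- **Scope of the 28 days:** "The concept of 28 days is applied to subjects without events that discontinued or completed the study". Ongoing subjects have no 28 days added.

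Safety data are to be "summarized descriptively by initial treatment group and combined Tofacitinib group". On capture of late events, Protocol 8.2 ends active SAE reporting 28 days after the last dose. After that, SAEs "should be reported to the sponsor if the investigator becomes aware of them".

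**The concern.** The exception widens the numerator only. A subject who stops treatment and stays event-free adds no time after day 28, while one whose cancer is found a year after stopping adds an event. The result is not a rate over any single period of observation. Nor can a reader tell how much of it comes from outside the counted time.

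A second, smaller problem is the person-time of the late case itself. The earlier-of rule and the death sentence both point to stopping the clock at day 28. The closing paragraph ties the 28 days to subjects without events, which suggests that a case's clock may run to the event. The death sentence also stands before the exception and may be only a general rule for censoring at death. Two programmers could compute different denominators.

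The description of the malignancy endpoints names NMSC twice inside one exclusion, so it is not certain which malignancy rates the exception covers.

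These are the gravest and rarest events in the primary analysis. They are reported by initial dose group as well as combined, so small counts are plausible, and small counts are where one added case matters most.

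**Working it through.** The documents state no incidence rate, event count or person-time total, so there is no planned figure to reproduce. The check is therefore general, with counts and person-years assumed where needed.

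**Notation.** *E* = subjects with a first event by last dose + 28 days. *L* = subjects with a first event after that. *PY* = person-years under the 28-day rule. The numerator counts unique subjects, so a late event in a subject already counted for that endpoint has no effect.

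**Step 1: late case's clock stopped at day 28.** Late cases already contribute their time up to day 28, so *PY* is the same with or without them.

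- Matched 28-day rate = *E*/*PY*
- SAP rate = (*E* + *L*)/*PY*
- Ratio = (*E* + *L*)/*E*, whatever *PY* is

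The exact Poisson limits for a count *n* are half the 2.5% chi-square quantile on 2*n* degrees of freedom and half the 97.5% quantile on 2*n* + 2. For *L* = 1 (ratios taken from unrounded limits):

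| *E* | Limits at *E* | Limits at *E* + 1 | Rate ratio | Lower-limit ratio | Upper-limit ratio |
|---|---|---|---|---|---|
| 0 | 0, 3.689 | 0.025, 5.572 | from 0 to 1/*PY* | – | 1.51 |
| 2 | 0.242, 7.225 | 0.619, 8.767 | 3/2 = 1.50 | 2.55 | 1.21 |
| 5 | 1.623, 11.668 | 2.202, 13.059 | 6/5 = 1.20 | 1.36 | 1.12 |
| 10 | 4.795, 18.390 | 5.491, 19.682 | 11/10 = 1.10 | 1.15 | 1.07 |
| 20 | 12.217, 30.888 | 12.999, 32.101 | 21/20 = 1.05 | 1.06 | 1.04 |

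On the rate scale, assume *PY* = 2,500, *E* = 10 and *L* = 2. The matched rate is 10/2,500 = 0.400 per 100 PY (95% limits 0.192 to 0.736). The SAP rate is 12/2,500 = 0.480 (0.248 to 0.838), a rise of 20%.

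**Step 2: late case's clock run to the event.** Let *t* be the years from day 28 to the event. For *L* = 1 the ratio is (*E* + 1)/*E* × *PY*/(*PY* + *t*). An event 1 year after the last dose gives *t* = 1 − 28/365.25 = 0.923; 3 years gives *t* = 2.923. With *E* = 5:

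| Assumed *PY* | *t* = 0.923 | *t* = 2.923 |
|---|---|---|
| 500 | 1.198 | 1.193 |
| 1,000 | 1.199 | 1.197 |
| 3,500 | 1.200 | 1.199 |

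Step 1 gives 1.200. The choice of clock therefore changes the factor by less than 1% here. To cancel the rise completely, *t* would have to reach *PY*/*E*: 500/5 = 100 years in the first row.

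**Step 3: what complete follow-up would give.** Assume *PY* = 2,500, *E* = 10 and a constant hazard of 0.400 per 100 PY, with 600 subjects followed fully for 1 year past day 28. Expected late first events are 0.004 × 600 = 2.4.

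- All-follow-up rate: 12.4/(2,500 + 600) = 0.400 per 100 PY
- SAP rate, clock stopped at day 28: 12.4/2,500 = 0.496 per 100 PY

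The hazard has not changed. The rise comes only from counting events without the time in which they arose.

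**The case against.** The strongest reply is that the exception is open and deliberate. Malignancy and death can declare themselves late, and counting them errs toward showing harm. No hypothesis is tested, the rates are descriptive, and the effect is zero if no late first event is captured. That a larger numerator exceeds the matched rate is close to self-evident. Against a fully ascertained all-follow-up rate the direction is uncertain, because capture after day 28 is passive (Protocol 8.2), CRF recording of AEs ends at the last visit, and no data are collected once consent for disclosure is withdrawn (Protocol 6.3). All of this stands. It limits the claim to a comparison with the matched 28-day rate, but it does not supply the missing person-time.

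It is also fair that the conflict over the late case's clock has almost no numerical effect, that the death sentence read alone gives a cap, and that the lower-limit ratio of 2.55 at *E* = 2 is a move from 0.242 to 0.619 expected events. The upper limit, the more cautious bound for safety, moves by 1.04 to 1.21 for *E* from 20 down to 2, and by 1.51 at *E* = 0. The NMSC wording looks like a slip and does not bear on the main point.

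Last, SAP Section 1 says that Section 6.2 was updated for incidence rates, and the visible Section 6.2 ends in redacted text. A further definition could lie there, so the finding concerns the visible text. What Section 8.2.4 itself says is not affected.

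**Conclusion.** The point holds. For mortality, malignancy and MACE, the visible SAP pairs an open-ended numerator with person-time that, for event-free subjects who have finished, ends at last dose + 28 days. Any late first event raises the rate and both limits above the matched 28-day rate. This is certain if the late case's clock stops at day 28, and true in any realistic case if it runs to the event. The factor is (*E* + *L*)/*E* under the cap, largest where counts are small. The actual size rests on event counts that the documents do not give.

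The mismatch is the main defect. The conflicting statements on late cases are a secondary one, worth settling because they affect programming rather than because they move the result. Nothing here shows that the SAP rate is too high against complete follow-up, or that harm is hidden. The problem is that the reported rate has no clear meaning for the gravest endpoints of the primary analysis, and it should be fixed.

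**What to change.** In SAP 8.2.4:

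1. Correct the NMSC wording so that the endpoints under the exception are listed plainly.
2. For mortality, malignancy excluding NMSC, NMSC and MACE, report a rate with events and person-time both cut at last dose + 28 days, beside the all-events rate.
3. Show separately the number of subjects whose first event came after day 28, by initial dose group and combined.
4. If the all-events rate is kept, label it as including events outside the counted person-time, and state one person-time rule for late cases, including late deaths.
5. Extend person-time to event, death or last contact only if this is done for all subjects and those dates exist.

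The cost is SAP wording plus an extra table row or listing. The matched rate uses dates that the SAP already needs. The drawbacks are two rates per endpoint to explain, and matched rates that may be slightly lower than the all-events rates. A true all-follow-up rate may not be feasible, because the last scheduled contact is the 4-week visit (±7 days; Protocol 6.2).

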8.2.5. Analyses of Patient reported Outcome (PRO) Endpoints

Descriptive summary statistics will be reported at scheduled visits in FAS, and four subpopulations; Maintenance Remission, Maintenance Failure, Other Maintenance Completers, and Induction Non-responders using the same methods as for the efficacy endpoints for IBDQ. ^{CCI} [REDACTED].

CCI [REDACTED]

CCI [REDACTED]

9. APPENDICES

Appendix 1. Definition of Analysis Visit Windows

Analysis visit windows will be used for efficacy variables, and for any safety displays that display by visit.

Visit Label	Target Day	Analysis Visit window
Baseline	Day 1	Up to Day 1
Month 1	Day 30	Days 2-45
Month 2	Day 60	Days 46-90
Month 4	Day 120	Days 91-150
Month 6	Day 180	Days 151-225
Month 9	Day 270	Days 226-315
Month 12	Day 360	Days 316-405
Month 15	Day 450	Days 406-495
Month 18	Day 540	Days 496-585
Month 21	Day 630	Days 586-675
Month 24	Day 720	Days 676-765
Month 27	Day 810	Days 766-855
Month 30	Day 900	Days 856-945
Month 33	Day 990	Days 946-1035
Month 36	Day 1080	Days 1036-1125
Month 39	Day 1170	Days 1126-1215
Month 42	Day 1260	Days 1216-1305
Month 45	Day 1350	Days 1306-1395
Month 48	Day 1440	Days 1396-1485
Month 51	Day 1530	Days 1486-1575
Month 54	Day 1620	Days 1576-1665
Month 57	Day 1710	Days 1666-1755
Month 60	Day 1800	Days 1756-1845
Month 63	Day 1890	Days 1846-1935
Month 66	Day 1980	Days 1936-2025
Month 69	Day 2070	Days 2026-2115
Month 72	Day 2160	Day 2116-2205
Month 75	Day 2250	Days 2206-2295
Month 78	Day 2340	Days 2296-2385
Month 81	Day 2430	Days 2386-2475
Month \geq 84	Day 2520	Days \geq 2476

If more than one observation from the same subject falls into the same window, the value closest to the target day will be used as the observation for that analysis visit. All observations will, however, be included in the listings.

For efficacy endpoints derived based on total Mayo score we will use the same windows from the above table although total Mayo score was not assessed at each visit.

Some PRO data or laboratory data were not scheduled to be assessed at each visit. In this case, the unscheduled 'windowed' visit will be moved to the next scheduled windowed visit for analysis and reporting.

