3. STUDY DESIGN

This is a Phase 3, multi-center, open-label study in subjects who have completed or demonstrated treatment failure in the maintenance study A3921096, or who were non-responders after completing induction studies A3921094 or A3921095. Approximately 900 subjects are expected to become eligible for the study. This study will continue up to approximately July 2020. Individual subject duration of participation will vary depending on when the subject was enrolled into the study and the end date of approximately July 2020. Therefore, the duration of participation for an individual subject may range from approximately 4 years to more than 7 years. If the study continues beyond Month 72 for an individual subject, the investigator should continue to follow the same visit schedule and study procedures outlined during the study visits of year 4.

Subjects who completed Study A3921096 or had early withdrawal due to treatment failure as defined in the A3921096 protocol may be eligible to enroll in this study, A3921139. In addition, subjects who complete induction Study A3921094 or A3921095 and are classified as non-responders may be eligible to enroll in this study. The eligibility of a subject for this study will be assessed based on study data collected at Week 8/9 of Study A3921094 or A3921095 (for non-responders) or the Week 52/53 visit (for completers) or early termination visit (early withdrawals due to treatment failure) of Study A3921096. The study data collected at the Week 8/9 visit for Study A3921094 or A3921095 (for non-responders) or the Week 52/53 visit or early termination visit of Study A3921096 will be recorded as the baseline data for Study A3921139.

Eligible subjects will be assigned to either tofacitinib 5 mg BID or 10 mg BID depending on whether the subject is in remission at baseline of Study A3921139. Remission is defined by a total Mayo score ≤ 2 with no individual subscore > 1 , and rectal bleeding subscore of 0. Eligible subjects who are in remission at Week 52 of Study A3921096 will be assigned to receive tofacitinib 5 mg BID. For treatment assignment at baseline, the central read assessment of the Mayo endoscopic subscore will be used to determine if a subject is in remission. Subjects who complete Study A3921096 but do not meet the remission definition

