2.1. Study Design

This is a Phase 3, multi-center, open-label study in subjects who have completed or demonstrated treatment failure in the maintenance study A3921096, or who were non-responders after completing 8 weeks of treatment in the induction Study A3921094 or A3921095. Approximately 900 subjects are expected to become eligible for the study. This study will continue up to approximately July 2020. Individual subject duration of participation will vary depending on when the subject was enrolled into the study and the study end date. Therefore, the duration of participation for an individual subject may range from approximately 4 years to more than 7 years. If the study continues beyond Month 72 for an individual subject, the investigator should continue to follow the same visit schedule and study procedures outlined during the study visits of year 4.

Subjects who completed Study A3921096 or had early withdrawal due to treatment failure as defined in the A3921096 protocol are eligible to enroll in this study, A3921139. In addition, subjects who complete 8 weeks of treatment in Study A3921094 or A3921095 and are classified as non-responders are eligible to enroll in this study. The eligibility of a subject for this study will be assessed based on study data collected at Week 8/9 of Study A3921094 or A3921095 (for non-responders) or the Week 52/53 visit (for completers) or early termination visit (early withdrawals due to treatment failure) of Study A3921096. The study data collected at the Week 8/9 visit for Study A3921094 or A3921095 (for non-responders) or the Week 52/53 visit or early termination visit of Study A3921096 will be recorded as the baseline data for Study A3921139.

Eligible subjects will be assigned to either tofacitinib 5 mg BID or 10 mg BID depending on whether the subject is in remission at baseline of Study A3921139. Remission is defined by a total Mayo score ≤ 2 with no individual subscore > 1 , and rectal bleeding subscore of 0. Eligible subjects who are in remission at Week 52 of Study A3921096 will be assigned to receive tofacitinib 5 mg BID. For treatment assignment, the central read assessment of the Mayo endoscopic subscores will be used to determine if a subject is in remission. Subjects who complete Study A3921096 but do not meet the remission definition or who are early

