- Be in stable remission on tofacitinib 10 mg BID for the 6 month period in Study A3921139 up to and including the baseline visit of Study A3921288, defined as meeting all the following criteria:
 - A partial Mayo score ≤ 2 , with no individual subscore > 1 and a rectal bleeding subscore of 0 at each study visit during the 6 month period in Study A3921139 prior to and at baseline of Study A3921288; AND
 - At least one assessment of remission based on Mayo score.
- Not be receiving any corticosteroids to treat their UC for at least 4 weeks prior to the baseline visit of Study A3921288.

[figure not shown]
Study A3921288 will evaluate the efficacy and safety of tofacitinib in subjects in stable remission on 10 mg BID who decrease the dose to and remain on 5 mg BID compared to subjects who remain on 10 mg BID.

All subjects who withdraw early or who complete this open-label study, with the exception of those subjects entering Study A3921288, will have a 4-week safety follow-up evaluation after the last dose of study medication.

Subjects will be required to remain on stable doses of their concomitant medications for UC during the study period. Subjects who enter this study on corticosteroids (eg, subjects who withdraw from Study A3921096 due to treatment failure or non-responders at the end of Study A3921094 or A3921095) will need to continue the steroid tapering regimen described in Study A3921096. If a subject requires rescue therapy or undergoes surgery, the subject should be withdrawn from the study and appropriate agents should be given at the discretion of the investigator.

Per protocol Amendment 11, Version 18 June 2019, the study investigator or designee will be required to ask each subject at each study visit if he/she has any newly-developed risk factors for PE, and if one is identified, the subject will need to have their tofacitinib dose adjusted to 5 mg BID if they are taking open label 10 mg BID.

Figure 1. Study Design

- Study visits will occur every 3 months after the first year until approximately July 2020.
- All subjects will have a 4-week follow-up evaluation after their last dose of study medication.

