8.2.3. Secondary CCI [REDACTED] Efficacy Analyses

All efficacy endpoints are considered as secondary CCI [REDACTED]. Descriptive summary statistics will be reported at scheduled visits in FAS, and subpopulations: maintenance

remission subpopulation, maintenance treatment failure subpopulation, other maintenance completers subpopulation, and induction non-responder subpopulation. However, the endpoints of proportion of subjects with dose increase from tofacitinib 5 mg BID to 10 mg BID will be summarized for maintenance remission subpopulation only.

For FAS or each subpopulation, the data will be summarized based on the following table:

Efficacy Analysis Population/Subpopulation	Treatment group (the default is the assigned dose for initial assignment in A3921139)	By group
FAS	Overall Tofacitinib 5 mg BID Tofacitinib 10 mg BID	Overall
Maintenance Remission subpopulation	Tofacitinib 5 mg BID	Overall By maintenance treatment (4 groups: 10 mg, 5 mg, placebo, 5mg+10mg)
Maintenance Treatment Failure subpopulation	Tofacitinib 10 mg BID	Overall By dose combination received in induction and maintenance (6 groups) and a 7th group of Tofacitinib 10 mg in induction and Tofacitinib 5 mg + placebo in maintenance
Other Maintenance Completers subpopulation	Tofacitinib 10 mg BID	Overall By maintenance treatment (4 groups: tofacitinib 10 mg, Tofacitinib 5 mg, placebo, Tofacitinib 10 mg and 5 mg combined)
Induction Non-responder subpopulation	Tofacitinib 10 mg BID	Overall By Induction treatment (Tofacitinib 10 mg, Placebo)

CCI [Redacted]

- [Redacted]
- [Redacted]
- [Redacted]
- [Redacted]

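### The Month ≥84 row in SAP Appendix 1 reports the Month 84 value for every subject who has one, so its label does not match what it shows

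*SAP*

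**What the plan says.** SAP Appendix 1 assigns each visit a closed window. From Month 9 on these are 90 days wide, and the last closed one is Month 81 at "Days 2386-2475". Everything from Day 2476 onward goes into a single row, Month ≥84, with target Day 2520 and no upper bound.

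One value per subject is analysed in each row: "If more than one observation from the same subject falls into the same window, the value closest to the target day will be used". Values not chosen are kept elsewhere: "All observations will, however, be included in the listings". On scope: "Analysis visit windows will be used for efficacy variables, and for any safety displays that display by visit".

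Follow-up past Month 84 is expected. SAP 2.1 says that "the duration of participation for an individual subject may range from approximately 4 years to more than 7 years", and its design figure notes that "Study visits will occur every 3 months after the first year until approximately July 2020". Protocol section 3 adds: "If the study continues beyond Month 72 for an individual subject, the investigator should continue to follow the same visit schedule" (that of year 4). SAP 8.2.3 promises that "Descriptive summary statistics will be reported at scheduled visits in FAS" and in the subpopulations.

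**The concern.** A row labelled Month ≥84 suggests a summary of data from Month 84 onward. With a fixed target at Day 2520 and the closest value chosen, it instead selects the earliest scheduled visit in an open interval. Scheduled visits after that have no row of their own.

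PMS remission and IBDQ total score of at least 170 are secondary endpoints that Protocol 2.2 defines over time, with no stop at Month 36. By-visit laboratory and vital-sign displays use the same windows. For these displays, what happens after a subject's Month 84 value is not summarised, although the label implies that it is.

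**Working it through.** **Inputs.** Targets, windows and selection rule: SAP Appendix 1. Visits every 3 months and a visit tolerance of ±7 days after the first year: Protocol Schedule of Activities. Imputation: SAP 7.1 to 7.3. The documents do not say whether sites count a month as 30 days or as a calendar month (30.4375 days on average), so both are shown.

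**1. Reproducing the grid.** Upper bound = (target + next target)/2, with 30 days per month. This matches all 29 rows from Month 1 to Month 81; for example (2340 + 2430)/2 = 2385 for Month 78. For Month 81, (2430 + 2520)/2 = 2475, so the last row starts at Day 2476, as stated. Continued by the same rule, Month 84 would close at (2520 + 2610)/2 = 2565.

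**2. Which value is chosen.** Distance from Day 2520:

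| Visit | 30-day months | Calendar months |
|---|---|---|
| Month 84 | 2520: 0 days | 2557: 37 days |
| Month 87 | 2610: 90 days | 2648: 128 days |
| Month 90 | 2700: 180 days | 2739: 219 days |
| Month 93 | 2790: 270 days | 2831: 311 days |

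With the ±7-day tolerance, Month 84 is at most 7 days (30-day) or 44 days (calendar) from target. Month 87 is at least 90 − 7 = 83 or 128 − 7 = 121 days away. An attended Month 84 visit is therefore always chosen over any later scheduled visit.

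**3. What SAP 7.1 does with this row.** Imputation runs to the last window whose lower bound the subject would have reached. The final lower bound in the table is Day 2476.

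| Subject | Content of the Month ≥84 row (efficacy) |
|---|---|
| Has a Month 84 value, attends later visits | Month 84 value |
| Has a Month 84 value, then leaves | Month 84 value; nothing is missing, so nothing is imputed |
| Missed Month 84, attended Month 87 | Month 87 value; in any other row a missed visit becomes a non-response (binary) or LOCF (continuous) |
| Left before Day 2476 but would have reached it | Non-response (binary) or LOCF (continuous); LOCF for both if the subject moved to A3921288 or the Japan surveillance study, or left because of approval in Japan |
| Early-termination visit in the window, no closer value | Early-termination value |

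Safety displays are observed-case (SAP 7.3), so for them only the selection rule matters.

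**4. Displays affected.** Under the year 4 schedule, which repeats, partial Mayo score, vital signs, hematology and chemistry are taken every 3 months and fasting lipids every 6. IBDQ is yearly, so the next scheduled one after Month 84 is Month 96.

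**5. Scheduled visits without a row, per subject.** Enrolment dates are not given. Assuming an end on 31 July 2020 and counting visits from Month 87 on:

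| Assumed entry | Months to end | Later scheduled visits |
|---|---|---|
| 30 Sep 2011 (original protocol date, outer bound) | 106.0 | 7 |
| 1 Jan 2012 | 103.0 | 6 |
| 1 Jul 2012 | 97.0 | 4 |
| 1 Jan 2013 | 90.9 | 2 |
| 1 Jul 2013 | 85.0 | 0 |

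**6. Can the 30-day grid simply be continued?** Not safely. It would give Month 87 = 2566–2655 and Month 90 = 2656–2745. By Month 90 a calendar visit has drifted 90 × 0.4375 = 39 days past its target. A visit 7 days late falls on about 2739 + 7 = Day 2746, outside that window. Closing Month 84 at Day 2565 is still safe, since 2557 + 7 = 2564.

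**The case against.** **What stands against the point.** Any cross-sectional row ignores what follows it: a Month 60 row takes no account of a relapse at Month 63. Pooling a sparse tail is a normal display choice, the study tests no hypotheses, and all values stay in the listings. This limits the importance of the point. It does not answer it, because Month 63 has its own row and Month 87 does not, and a closed Month 84 row would not carry the ≥ sign.

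**Stronger readings that a reader might infer, and why the documents do not support them.**

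- *The row never contains anything after Month 84, and dropouts never count.* A missing Month 84 lets a later value in, and dropouts before Day 2476 who would have reached it are imputed.
- *The row is offered as the trial's longest-term result.* The SAP does not say so; that would be inferred from the label.
- *Late follow-up is confined to listings.* SAP 8.2.4 summarises adverse events over the whole treatment period. Incidence rates run to last dose plus 28 days, and later events also count for mortality, malignancy and MACE endpoints. None of this uses visit windows.
- *The row is biased in favour of the drug.* The rule drops regained remissions as well as relapses, and SAP section 2 describes UC as alternating between the two. Only the uncounted later NRI dropouts push one way, and their number is unknown.
- *A definite percentage is misclassified.* Assuming that 2% to 5% per quarter lose remission or leave gives 1 − 0.98³ = 5.9% to 1 − 0.95³ = 14.3% after three visits. The documents give no such rate, and the sum credits no regained remission.
- *Three of four values are lost on every measure up to Month 93.* That fits three-monthly measures only. IBDQ has no scheduled value at Months 87, 90 or 93, and lipids are six-monthly.

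**Conclusion.** The point holds as a mismatch between label and content. For every subject with a Month 84 value, the Month ≥84 row is a Month 84 row, and nothing in SAP 7.1 brings in later visits, relapses, recoveries or dropouts. For subjects who missed Month 84, it mixes in later times and bypasses the imputation used in other rows.

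It is confined to by-visit displays of partial Mayo score and PMS remission, laboratory values and vital signs, and to scheduled IBDQ from Month 96. Adverse event summaries, incidence rates and the Mayo-score endpoints at Months 2, 12, 24 and 36 are untouched.

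The selection result rests only on Appendix 1 and the ±7-day tolerance, and it is the same on 30-day and calendar months. The effect on any reported percentage, and its direction, cannot be derived because the number of subjects followed past Month 84 is not given. Between 0 and 7 scheduled visits per subject lack a row, depending on the assumed entry date; 7 is an outer bound.

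**What to change.** In SAP Appendix 1, close Month 84 at Days 2476–2565 and add a row for each later scheduled visit (Month 87, 90, 93 and so on to the last). Set the bounds between the added rows at midpoints of the visit days actually scheduled. On calendar months that gives:

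- Month 87: Days 2566–2693, since (2648 + 2739)/2 = 2693.5
- Month 90: Days 2694–2785, since (2739 + 2831)/2 = 2785
- Month 93: Days 2786–2876, since (2831 + 2922)/2 = 2876.5

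If the sites' schedule runs on 30-day months, use 2655, 2745 and 2835 as the upper bounds. Apply the NRI and LOCF rules of SAP 7.1 to each efficacy row, keep safety displays observed-case, and show N in every row.

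If late N is too small to display, still close the window at Day 2565, label the row Month 84, and state the number followed beyond it.

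The cost is a few extra rows in the SAP and programs, and some of them will be sparse. The relabelling option needs only the closed bound, the new label and one count.
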